4.6 Missed Visits

In general, missed dialysis session visits will not be replaced. If a patient misses a mid-week dialysis session, where a study treatment visit was scheduled to occur, the missed study visit procedures will be performed during the next mid-week dialysis session and subsequent visits and follow-up visit will occur as planned. However, if the patient fails to return for that mid-week dialysis session and also misses the subsequent week (a third mid-week session), then the patient will be terminated from the study. Study termination also applies if the patient misses 3 consecutive study treatments (i.e. missing a full week of dialysis). Reasons for missed visits will be captured on the eCRF.

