5.2 Baseline Definition

Baseline measure for laboratory assessments and vital signs is defined as the last predialysis non-missing value obtained prior to dialysis on the day of the first study treatment. The final measure for laboratory assessments is defined as the last value captured during study treatment sessions (Week 24). If laboratory assessment on Week 24 is not applicable, the value on end of study visit (pre-dialysis) will be considered as final measurement.

Baseline measure for demographics, physical examination, general medical history and renal medical history is obtained during screening.

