5.6 Safety Measures

The primary safety endpoint is the pre-dialysis serum level of albumin after 24 weeks of treatment.

Secondary safety endpoints include:

- Pre-dialysis serum albumin measured on the first day of treatment and after every 4 weeks of treatment.
- Pre-dialysis Factor VII (MW = 50 kDa), Protein C (MW = 53-62 kDa) and Factor II (MW = 72 kDa) measured on the first day of treatment, after 4 weeks and after 24 weeks of treatment.
- Pre-dialysis Vitamin A measured on the first day of treatment, after 4 weeks and after 24 weeks of treatment.
- nPNA (nPCR) calculated after every 4 weeks of treatment.
- Change from baseline to final measure in chemistry and hematology laboratory tests (see Table 7 in Section 9.3).
- Monitoring of adverse events (AEs), serious adverse events (SAEs) and product complaints (PCs) for Baxter related devices.

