7.2 Handling of Missing Data

7.2.1 General

Missed dialysis session visits will not be replaced. For dialysis sessions besides in Visit 8 Week 24, if a patient misses a mid-week dialysis session, where a study treatment visit was scheduled to occur, the missed study visit procedures will be performed during the next dialysis session and subsequent visits and follow-up visit will occur as planned. However, if the patient fails to return for that mid-week dialysis session and also misses the subsequent week (a third mid-week session), then the patient will be terminated from the study. Study termination also applies if the patient misses 3 consecutive study treatments (i.e. missing a full week of dialysis). Any dialysis session in Visit 8 Week 24 can not be collected behind schedule. Reasons for missed visits will not be captured separately but will be part of protocol deviation and/or as study discontinue reason if the patient being terminated from the study. Reasons for any other missing data besides missed visits will also be addressed via protocol deviations. A listing of protocol deviations will include a field showing whether the deviation lead to missing data. A protocol deviation table will summarize the number of missing data points in total and categorized by protocol deviation classification (major or minor).

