7.2.2 Primary Analysis

The primary analyses will be performed using a multiple imputation approach. Multiple imputations using SAS Proc MI will be implemented to impute missing data under the missing at random assumption and the data sets generated will be analyzed using SAS Proc MIANALYZE.⁹

The multiply imputed data sets are then analyzed by using standard procedures for complete data and combining the results from these analyses. Multiple imputation does not attempt to estimate each missing value through simulated values, but rather to represent a random sample of the missing values. This process results in valid statistical inferences that properly reflect the uncertainty due to missing values.

Multiple imputation inference involves three distinct phases:

- 1. The missing data are filled in m times to generate m complete data sets.
- 2. The m complete data sets are analyzed by using standard procedures.
- 3. The results from the m complete data sets are combined for the inference.

The MI procedure is a multiple imputation procedure that creates multiply imputed data sets for incomplete p-dimensional multivariate data. It uses methods that incorporate appropriate variability across the m imputations. The imputation method of choice depends on the patterns of missingness in the data and the type of the imputed variable.

A data set with variables Y_1, Y_2, \ldots, Y_p (in that order) is said to have a monotone missing pattern when the event that a variable Y_j is missing for a particular individual implies that all subsequent variables $Y_k, k > j$, are missing for that individual.

For data sets with monotone missing patterns, the variables with missing values can be imputed sequentially with covariates constructed from their corresponding sets of preceding variables. The regression method (Rubin 1987, pp. 166-167)¹⁰ for imputation will be used. Using the primary safety analysis as an example, if a subject is missing serum albumin values at weeks 20 and 24, a regression model is first fitted using the non-missing values prior to week 20 (baseline, weeks 4, 8, 12, and 16) in order to impute the missing value for week 20. This method is then repeated in order to impute the missing value for week 24 using the non-missing values of the prior weeks plus the newly imputed value for week 20.

Twenty (20) complete data sets will be analyzed for the multiple imputation of the primary endpoint data.

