12.1 Primary Analysis

For the primary efficacy endpoint of RR of λ FLC after 24 weeks of treatment, let μ_T denote the Theranova 400 dialyzer RR of λ FLC mean at 24 weeks and let μ_R denote the Elisio-17H dialyzer RR of λ FLC mean at 24 weeks. Then the null hypothesis to demonstrate superiority can be expressed as:

Ho: μ_T - $\mu_R = 0$. The alternative hypothesis is expressed as Ha: μ_T - $\mu_R \neq 0$.

The primary safety analysis will be conducted first. If the primary safety analysis demonstrates non-inferiority, an ANCOVA model with fixed effects of treatment and site will be used to generate a two-sided 95% CI for the difference in treatment means (μ_T - μ_R). If the lower bound is > 0 then superiority will be demonstrated. The statistical testing of the primary efficacy endpoint of the reduction ratio (RR) of λ FLC after 24 weeks of

treatment is contingent upon the outcome of the analysis of the primary safety endpoint and will only be conducted once non-inferiority could be established for the primary safety endpoint. This hierarchical testing approach guarantees that the overall Type I error is controlled at a two-sided 0.05 significance level.

The primary efficacy analyses will be performed using a multiple imputation approach. Multiple imputations using SAS Proc MI will be used to impute missing data under the missing at random assumption and the data sets generated will be analyzed using SAS Proc MIANALYZE (for more detail on missing data imputation see Section 7.2.2).

Twenty (20) complete data sets will be analyzed for the multiple imputation of the primary endpoint data.

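### The protocol and SAP disagree on whether a missed Week 24 visit can be made up, and the primary albumin imputation makes no use of the albumin drawn at the end-of-study visit

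*SAP*

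**What the plan says.** **Making up a missed visit.** Under Protocol 4.6, when a mid-week study visit is missed, "the missed study visit procedures will be performed during the next mid-week dialysis session", with later visits and the follow-up visit unchanged. No visit is excepted. SAP 7.2.1 opens its rule with "For dialysis sessions besides in Visit 8 Week 24, if a patient misses a mid-week dialysis session", so Week 24 falls outside it, and then adds: "Any dialysis session in Visit 8 Week 24 can not be collected behind schedule". For the other visits it says "the missed study visit procedures will be performed during the next dialysis session", which drops the mid-week condition. SAP section 10, which records changes from the protocol, lists neither difference. Table 1 and Table 2 of the SAP label Week 24 as Visit 7 and show no Visit 8.

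**What the visit carries.** SAP 5.6: "The primary safety endpoint is the pre-dialysis serum level of albumin after 24 weeks of treatment". SAP 12.1 defines primary efficacy as the λ FLC reduction ratio "after 24 weeks of treatment, let μ_T denote the Theranova 400 dialyzer RR of λ FLC mean at 24 weeks".

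**The end-of-study albumin.** Table 2 and Table 7 of the SAP schedule a pre-dialysis albumin at the end-of-study visit. When Week 24 is unavailable, SAP 5.2 says "the value on end of study visit (pre-dialysis) will be considered as final measurement", and SAP 11.3 repeats this for chemistry and hematology. SAP 7.2.2 takes another route for the primary analysis. Its worked example fits a regression on earlier visits "in order to impute the missing value for week 20", then imputes Week 24 from the earlier weeks plus that imputed value. SAP 11.1 refers back to 7.2.2 and does not mention the end-of-study value.

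**The concern.** Two gaps meet at one visit.

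First, a site following the protocol may draw a Week 24 sample late, while the SAP says this cannot be done. Nothing states how such a sample is classified. SAP 7.5 tabulates by the planned time point entered in the eCRF, so it could count as Week 24. The same section confines unscheduled visits to listings, so it could also drop out of the tables. SAP 6.3 removes patients from the PPS for improper assessment of the primary endpoint, so it could count in the FAS but not in the PPS. In an open-label trial this choice should be fixed before anyone sees which patients it affects.

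Second, a patient without a Week 24 albumin but with an end-of-study albumin would have an observed final value in the shift table and an imputed value in the non-inferiority test. That test would then lean more on the missing-at-random model than the collected data require.

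**Working it through.** **The plan's own figures.** Margin: 0.05 × 35.3 = 1.765 (Protocol 10.2, SAP 11.1). With SD 3.7 and 70 per group, the noncentrality is 1.765 / (3.7 × √(2/70)) = 1.765 / 0.625 = 2.82 on 138 df. One-sided α = 0.025 gives power 80.0%, as stated. Allowing for dropout, 70 / 0.85 = 82.4, rounded up to 83 per group and 166 in total. The λ FLC figure also reproduces: difference 4.56, SD 8.26, 70 per group gives 90.0%. The design arithmetic is not in question.

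**Where the sessions fall.** Day 1 is a mid-week session (Protocol 3.1) and treatment is three times weekly.

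| Event | Source | Day |
|---|---|---|
| Session 73 = 24 × 3 + 1, the last study treatment and the Week 24 visit | Protocol 5.8 (73 treatments) | 1 + 24 × 7 = 169 |
| End-of-study visit: next HD session, first non-study treatment | Protocol 3.1, 8.6 | 171 (assuming the usual two-day step after a mid-week session) |
| Make-up under Protocol 4.6: next mid-week session | Protocol 4.6 | 1 + 25 × 7 = 176 |

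Protocol 8.5 heads the treatment period as Day 1 to Day 168, one day short of session 73; the count of 73 fits Day 169. Both schedules also note that all sampling visits are mid-week, which read literally would move the end-of-study draw as well. I follow Protocol 3.1 and 8.6 because they address that visit directly.

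**What follows for each endpoint.**

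- *Albumin.* A protocol make-up falls 7 days late and 5 days after the planned end-of-study visit. The end-of-study sample is pre-dialysis, so it precedes the first non-study treatment and comes one session after Week 24. If only the draw was missed, it is a close substitute. If session 73 itself was missed, the last study session was on Day 167, and the gap before the sample is 4 days instead of 2.
- *λ FLC.* The reduction ratio describes one session (SAP Appendix 1). A ratio from a non-study session would not measure the randomized dialyzer. Table 2 of the SAP has no end-of-study λ FLC and no post-dialysis sample on Day 1, so the only earlier ratio is Week 4, 20 weeks before.

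**What the imputation can use.** SAP 7.2.2 builds each regression from the variables that precede the one being imputed. The end-of-study albumin comes after Week 24 in time, so in visit order it is not a predictor. A patient with Week 24 missing and end of study observed also breaks the monotone pattern that the regression method assumes.

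**The case against.** The strongest defence is that the Week 24 exception is deliberate. By Day 176 planned study treatment is over, and Protocol 4.6 itself keeps the follow-up visit on schedule, so its make-up rule is hard to apply to the last visit. This stands. It explains why the rule might differ, but not why the change is undeclared or why the protocol was left as it is. For the same reason, the absence of an end-of-study λ FLC sample is not a defect.

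A reader might infer that protocol-compliant primary samples are set to missing or discarded. The documents do not say so. SAP 7.2.1 restricts collection, no sentence voids a sample already taken, and SAP 7.5 would tabulate it as entered. The defect is the lack of a rule.

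It can also be said that SAP 7.2.2 offers an example, not an exclusion. That is fair: the end-of-study albumin is passed over by silence and by the ordering of the variables. Whether the LOCF analysis in SAP 7.2.3 may use it is equally unstated.

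A reader might further infer a power loss. If 5% of patients remaining after dropout lost Week 24 (an assumed rate), 83 × 0.85 × 0.95 = 67 per group would remain, and an unadjusted complete-case t-test would have 78.3% power. That figure does not describe this plan. The primary analysis keeps all randomized patients through multiple imputation and adjusts for baseline albumin. With an assumed baseline correlation of 0.5, even the complete-case figure is 88.6% at that loss. No fall from 80% to 78% is supported.

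'Visit 8' is a numbering slip. The words Week 24 identify the visit.

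**Conclusion.** The point holds as a gap in endpoint definition and missing-data handling. The two documents give different rules for the visit that carries both primary endpoints, the difference is undeclared, and the status of a late sample is undetermined. The primary albumin analysis, as written, makes no use of a scheduled observation one session later that the SAP trusts elsewhere.

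The size is limited to patients without a Week 24 sample. The documents give neither the rate of such patients nor the correlation between visits, so neither the gain in precision nor any effect on power can be computed; I expect both to be small. The benefit is less reliance on imputation in the non-inferiority test. The albumin argument assumes the end-of-study visit is the next HD session, and it does not extend to λ FLC.

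**What to change.** 1. Reconcile Protocol 4.6 and SAP 7.2.1 so that one rule governs Week 24, list the change in SAP section 10, and correct the visit number to Visit 7. In the same edit, settle the differing make-up timing for the other visits. State how a late Week 24 sample is classified in the FAS and in the PPS.
2. In SAP 7.2.2 and 11.1, include observed end-of-study and early-termination pre-dialysis albumin as predictors in the imputation model, placed at the time they were drawn. Use a method that allows a non-monotone pattern, such as fully conditional specification or MCMC.
3. For patients who completed the treatment period and missed only the Week 24 draw, the end-of-study albumin may stand as the Week 24 value, at least in a sensitivity analysis. State whether LOCF may use it.
4. Do not let an early-termination albumin stand as the Week 24 value. For a patient who stops at Week 6, for instance, that would carry a short-exposure value into a 24-week test. If albumin falls with cumulative exposure, this could favour non-inferiority.

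The cost is wording, slightly more imputation programming, and a one-session time shift for a few values, which can be flagged. No new samples are needed.

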7.2.2 Primary Analysis

The primary analyses will be performed using a multiple imputation approach. Multiple imputations using SAS Proc MI will be implemented to impute missing data under the missing at random assumption and the data sets generated will be analyzed using SAS Proc MIANALYZE.⁹

The multiply imputed data sets are then analyzed by using standard procedures for complete data and combining the results from these analyses. Multiple imputation does not attempt to estimate each missing value through simulated values, but rather to represent a random sample of the missing values. This process results in valid statistical inferences that properly reflect the uncertainty due to missing values.

Multiple imputation inference involves three distinct phases:

- 1. The missing data are filled in m times to generate m complete data sets.
- 2. The m complete data sets are analyzed by using standard procedures.
- 3. The results from the m complete data sets are combined for the inference.

The MI procedure is a multiple imputation procedure that creates multiply imputed data sets for incomplete p-dimensional multivariate data. It uses methods that incorporate appropriate variability across the m imputations. The imputation method of choice depends on the patterns of missingness in the data and the type of the imputed variable.

A data set with variables Y_1, Y_2, \ldots, Y_p (in that order) is said to have a monotone missing pattern when the event that a variable Y_j is missing for a particular individual implies that all subsequent variables $Y_k, k > j$, are missing for that individual.

For data sets with monotone missing patterns, the variables with missing values can be imputed sequentially with covariates constructed from their corresponding sets of preceding variables. The regression method (Rubin 1987, pp. 166-167)¹⁰ for imputation will be used. Using the primary safety analysis as an example, if a subject is missing serum albumin values at weeks 20 and 24, a regression model is first fitted using the non-missing values prior to week 20 (baseline, weeks 4, 8, 12, and 16) in order to impute the missing value for week 20. This method is then repeated in order to impute the missing value for week 24 using the non-missing values of the prior weeks plus the newly imputed value for week 20.

Twenty (20) complete data sets will be analyzed for the multiple imputation of the primary endpoint data.

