5.3 Sample Size

The sample size for this study is driven by the primary safety endpoint. The sample size calculation was performed using PASS® 15.0.1 software, procedure Non-Inferiority Tests for the difference between Two Means. Copyright© 2017, NCSS, LLC. All Rights Reserved. The power is based on a t-test with a one-sided alpha level of 0.025 where the true difference in means is assumed to be zero (0) and the non-inferiority margin is 5%.

Pre-dialysis serum albumin was not evaluated in the previous Theranova 400 dialyzer HD study, only the mass (G) of albumin in the dialysate was assessed. However, a study published in PLoS ONE⁶ did use a prototype of the Theranova dialyzer (MCO-CI) where in pre-dialysis albumin levels were collected after a month of therapy and, based on these data, a mean and standard deviation (SD) of 35.3 and 3.7 was observed. Comparable pre-dialysis albumin levels are expected with both study dialyzers and with a sample size of 70 patients per group, a t-test with a 0.025 one-sided significance level will have 80% power to demonstrate non-inferiority of the Theranova 400 dialyzer compared to the Elisio-17H dialyzer as assessed by pre-dialysis serum albumin with a non-inferiority margin of 5%. To allow for 15% of patients to drop out, a total of 166 patients will be randomized 1:1 to treatment with the Theranova 400 dialyzer or treatment with the Elisio-17H dialyzer (i.e., 83 patients per group).

A previously conducted Theranova 400 dialyzer prototype HDF study (Comparison of the Clinical Performance of Two Theranova 400 Dialyzer Prototypes in Hemodialysis Mode with the Performance of a High-Flux Dialyzer in Hemodialysis Mode and a High-Flux Dialyzer in High-volume Hemodiafiltration Mode – A Pilot Study, registered at clinicaltrials.gov, NCT02377622) was used to obtain λ FLC reduction ratio mean and standard deviation (SD) of 37.8 and 8.26. With a total sample size of 140 evaluable subjects as determined based on the primary safety endpoint (70 in the Theranova 400 dialyzer treatment group and 70 in the Elisio-17H dialyzer treatment group), a difference of 4.56 in the λ FLC reduction ratio in favor of the Theranova 400 dialyzer can be detected with 90% power at a two-sided 0.05 significance level using a two-sided two-sample t-test assuming equal variances. Including 15% drop out, a total sample size of 166 (83 per treatment group) need to be enrolled into this study.

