7.2.3 Sensitivity Analysis

The impact of missing data on the primary safety and efficacy analyses will be further explored as sensitivity analyses using observed data as well as last observation carried forward (LOCF).

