9.3 Clinical Laboratory Evaluations

- Date and time lab sample collected (listing only)
- Initial / re-test (listing only)
- Accession / sample number (listing only)

Table 7: List of Laboratory Tests

(Test on screening pre-dialysis):

- β-hCG (if applicable)
- Hepatitis A, B and C
- Human Immunodeficiency Virus

(Test on screening pre-dialysis, 1st treatment day pre-dialysis, week 4 pre-/post-dialysis and week 24 pre-/post-dialysis):

- λ FLC
- κ FLC

(Test on 1st treatment day pre-dialysis, week 4 pre-/post-dialysis and week 24 pre-/post-dialysis):

- β2-microglobulin
- CFD
- IL-6
- TNFα

(Test on 1st treatment day pre-dialysis, week 12 predialysis, week 24 pre-dialysis and end of study predialysis):

- Factor II
- Factor VII
- Protein C

(Test on 1st treatment day pre-dialysis, week 4 pre-dialysis, week 24 pre-dialysis and end of study pre-dialysis):

• Vitamin A

(Test on every visit pre-dialysis besides end of study pre-dialysis):

• hs-CRP

Serum Chemistry: (Test on every visit pre-dialysis):

• Albumin

(Test on every visit pre-/post-dialysis besides 1st treatment day and end of study):

• BUN

(Test on screening pre-dialysis, 1st treatment day pre-dialysis, week 12 pre-dialysis and end of study pre-dialysis):

• Phosphorus

Coagulation (test on screening pre-dialysis, week 12 pre-dialysis and end of study pre-dialysis):

- Prothrombin time
- INR
- Activated partial thromboplastin time

Comprehensive Metabolic Panel (test on screening pre-dialysis, 1st treatment day pre-dialysis, week 12 pre-dialysis and end of study pre-dialysis):

• Bicarbonate

Hematology (test on screening pre-dialysis, 1st treatment day pre-dialysis, week 12 pre-dialysis and end of study pre-dialysis):

- Calcium
- Chloride
- Creatinine
- Glucose
- Sodium
- Potassium

Liver Function (test on screening pre-dialysis, week 12 pre-dialysis and end of study pre-dialysis):

- Alkaline phosphatase
- ALT; SGPT
- AST; SGOT
- Direct bilirubin
- Gamma-glutamyl transferase
- Globulin
- Total bilirubin
- Total protein

- Hematocrit
- Hemoglobin
- Mean corpuscular hemoglobin
- Mean corpuscular hemoglobin concentration
- Mean corpuscular volume
- Platelet count
- Red blood cell count
- White blood cell count with differential

Lipids (test on screening pre-dialysis, 1st treatment day pre-dialysis, week 12 pre-dialysis and end of study pre-dialysis):

- Total cholesterol
- HDL cholesterol
- LDL cholesterol
- Triglycerides

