11.1 Primary Analysis

For the primary safety endpoint of pre-dialysis serum albumin after 24 weeks of treatment, let μ_T denote the Theranova 400 dialyzer pre-dialysis serum albumin mean and let μ_R denote the Elisio-17H dialyzer pre-dialysis serum albumin mean. Then the null hypothesis to demonstrate non-inferiority using a 5% margin can be expressed as:

Ho: μ_T - $\mu_R \leq -1.765$. The alternative hypothesis is expressed as Ha: μ_T - $\mu_R > -1.765$.

An ANCOVA model with fixed effects of treatment and site and the continuous fixed covariate of baseline pre-dialysis serum albumin will be used to generate a two-sided

95% confidence interval (CI) for the difference in treatment means (μ_T - μ_R). If the lower bound is > -1.765 then non-inferiority will be demonstrated.

The primary safety analyses will be performed using a multiple imputation approach. Multiple imputations using SAS Proc MI will be used to impute missing data under the missing at random assumption and the data sets generated will be analyzed using SAS Proc MIANALYZE (for more detail on missing data imputation see Section 7.2.2).

Twenty (20) complete data sets will be analyzed for the multiple imputation of the primary endpoint data.

The analysis of the primary safety endpoint will be carried out on both the FAS and PPS. The analysis using the PPS will be used as a supportive analysis.

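### SAP 7.2.2 does not put treatment arm in the imputation model for the primary endpoints; run as its example is written, imputation pools the arms and pulls a constant or growing albumin deficit toward non-inferiority

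*SAP*

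**What the plan says.** SAP 7.2.2 plans multiple imputation under missing at random, using the monotone regression method and 20 data sets. Its general rule is that missing values are "imputed sequentially with covariates constructed from their corresponding sets of preceding variables". Its worked example concerns a patient whose last two scheduled albumin results (week 20, week 24) were not obtained. There, "a regression model is first fitted using the non-missing values prior to week 20 (baseline, weeks 4, 8, 12, and 16", and week 24 is then imputed from the same values plus the imputed week 20. Protocol 10.5 gives the same example. Neither document names arm as a predictor or says that imputation is run within arm.

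The analysis models do contain arm. For albumin (SAP 11.1): "An ANCOVA model with fixed effects of treatment and site and the continuous fixed covariate of baseline pre-dialysis serum albumin will be used". For the λ FLC reduction ratio (SAP 12.1): "an ANCOVA model with fixed effects of treatment and site will be used to generate a two-sided 95% CI". On imputation, both sections only point back; SAP 11.1 says "for more detail on missing data imputation see Section 7.2.2".

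The full analysis set with imputation decides both primary tests. SAP 7.2.3 adds observed-data and LOCF sensitivity analyses.

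**The concern.** If arm is left out, the imputation model is narrower than the analysis model. A missing Theranova value is drawn from a relation averaged over both dialyzers, and so is a missing Elisio value, so the imputed patients carry less of the true difference than the observed ones. In a superiority test that dilution costs the sponsor power. In a non-inferiority test it can move the estimate toward success.

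Albumin non-inferiority is the primary safety claim and the gate to the efficacy test. Protocol 1.2 acknowledges that Theranova takes out more albumin per session than high-flux devices, so a true deficit is the case this test has to detect.

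**Working it through.** **The plan's own figures.** Inputs from SAP 5.3: mean 35.3 g/L, SD 3.7, one-sided alpha 0.025, 80% power, 15% dropout.

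- Margin: 0.05 x 35.3 = 1.765 g/L.
- Normal approximation: n = 2(1.960 + 0.842)² x 3.7² / 1.765² = 69 per arm. The noncentral t gives 80.02% power at 70 per arm.
- Dropout: 70 / 0.85 = 82.4, so 83 per arm and 166 in total.
- λ FLC: a difference of 4.56 with SD 8.26 and 70 per arm gives 90.03% power.

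All of these reproduce.

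**Mechanism.** Suppose 15% drop out at random in each arm, the true difference is -1.765, and the pooled model gives the dropouts an imputed difference of size d. The shift toward zero is then 0.15 x (1.765 - d).

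- Ceiling: if earlier albumin carries none of the deficit, d = 0 and the shift is 0.15 x 1.765 = 0.26 g/L.
- A shift of 0.06 corresponds to d = 1.765 - 0.06/0.15 = 1.37: earlier visits carry most of a constant deficit when dropout is late.
- A shift of 0.21 corresponds to d = 1.765 - 0.21/0.15 = 0.37: they carry little of it when dropout is early.
- If the deficit was deeper earlier, d can exceed 1.765 and the shift reverses.

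**Simulation.** Shifts come from 300,000 patients per arm. Error rates come from 5,000 trials per scenario with 83 per arm, SD 3.7, seven albumin visits, random monotone 15% dropout, 20 proper regression imputations, Rubin's rules, and ANCOVA on arm, baseline and 30 sites (Monte Carlo error 0.2-0.3 points). Not in the documents, and therefore assumed: visit correlation (constant 0.65, or 0.85 per visit decaying), the course of the deficit, and dropout timing. Ranges cover both correlation patterns. Every non-zero course reaches -1.765 at week 24.

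| Course of deficit | Dropout | Shift toward non-inferiority, arm omitted (g/L) | False non-inferiority, arm omitted |
|---|---|---|---|
| Constant | Week 24 only | 0.03-0.05 | not simulated |
| Constant | Weeks 20 and 24 | 0.06 | 2.3-2.6% |
| Constant | Spread evenly | 0.11-0.12 | 2.6-3.0% |
| Constant | Before week 8 | 0.19-0.21 | 3.1-3.8% |
| Growing (linear, or from week 16) | Week 24 only | 0.07-0.21 | not simulated |
| Growing | Weeks 20 and 24 | 0.13-0.24 | 3.1-5.6% |
| Growing | Spread evenly | 0.18-0.25 | 4.0-5.6% |
| Growing | Before week 8 | 0.25-0.26 | 4.0-5.5% |
| Plateau by week 8 | All timings | 0.03-0.24 | 2.4-4.7% |
| Twice as deep early, then recovering | Weeks 20 and 24 | 0.03-0.06 in the opposite direction | 1.2-1.7% |
| Recovering | Spread evenly | 0.02-0.03 | 1.8-2.0% |
| Recovering | Before week 8 | 0.14-0.15 | 3.3% |
| No difference | - | 0.00 | - |

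With arm in the imputation model, false non-inferiority is 2.1-2.9%. With spread dropout, mean estimates without and with arm are -1.65 vs -1.77 and -1.64 vs -1.75 for a constant deficit (constant and decaying correlation), and -1.54 vs -1.75 and -1.57 vs -1.75 for a linear one. The observed-data analysis gives -1.75 to -1.77 and 2.0-2.9%.

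**Second simulation, other assumed correlations** (constant 0.6 and 0.8, decaying 0.9; site omitted; 2,400 trials). With spread 15% dropout and arms pooled, a constant deficit is estimated at -1.65 to -1.67 with 2.5-3.5% false non-inferiority, and a growing one at -1.55 to -1.61 with 3.0-5.1%. With arm included, estimates are -1.75 to -1.78 and the error is 1.7-2.7%. At 25% dropout and correlation 0.6, pooling gives 3.3% (constant) and 6.3% (growing).

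**λ FLC.** SAP Table 7 schedules samples at "week 4 pre-/post-dialysis and week 24 pre-/post-dialysis" and no post-dialysis sample on the first treatment day, so the only earlier reduction ratio is week 4. Inputs: true difference 4.56, SD 8.26, 2.5% lost before week 4 and 15% by week 24, ANCOVA on arm and 30 sites, 4,000 trials. At assumed correlations of 0.3, 0.5 and 0.7, the estimate without arm is 4.08, 4.19 and 4.29, against 4.56-4.57 with arm. Power is 86.8%, 88.3% and 90.5% without arm, against 90.2%, 90.6% and 91.9% with it.

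**The case against.** The SAP is silent rather than wrong. It never defines the ordered variables as albumin only, the weeks 20 and 24 text is an example, and arm, being fully observed, could be listed first without departing from 7.2.2. This stands: the harm arises only if the program follows the example literally. But the example is the only list of predictors given, and the choice changes the statistic that decides the trial.

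The effect can be negligible. For a constant deficit with weeks 20 and 24 missing, which is the SAP's own dropout pattern, 2.3-2.6% cannot be told apart from 2.1-2.9%. This also stands. Clear inflation needs a growing or late-onset deficit or, more modestly, early dropout or high correlation. Those courses are assumptions, and nothing in the documents supports a deficit that begins at week 16.

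A deficit may not exist. Protocol 1.2 also says that albumin sieving is below 1% and that plasma albumin depends mainly on synthesis, and the sample size is set "where the true difference in means is assumed to be zero (0) and the non-inferiority margin is 5" percent. Under a zero difference there is no bias. The test exists, however, to guard against the other case.

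Other analyses would show a discrepancy: the observed-data analysis, the supportive per-protocol analysis of patients treated for 24 weeks, and the albumin mixed model with treatment in it (though with no treatment-by-visit term). The attempted End of Study albumin could also reduce missingness if the SAP 5.2 final-measure rule reaches the primary endpoint, which is not explicit. These are useful checks, but none of them decides non-inferiority.

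**Conclusion.** The concern holds. Followed as written, the imputation model omits the treatment term that both primary ANCOVAs contain. At a true difference of -1.765 g/L with 15% dropout, the pull toward non-inferiority for a constant deficit is about 3% of the margin (0.06/1.765) with weeks 20/24 dropout and up to 12% (0.21/1.765) with early dropout. For a growing deficit it reaches the ceiling of 15% of the margin, and the one-sided 2.5% error can roughly double, to 5.6%. The direction reverses or nearly vanishes for a recovering deficit unless dropout is early, and there is no bias at zero difference. For λ FLC the omission costs the sponsor some power and does not inflate a false efficacy claim.

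Confidence in the omission and in the mechanism is high. The sizes rest on the assumed correlations, deficit courses and dropout timings, with random dropout at the same rate in both arms. The point should be fixed: it is moderate in size, but it touches the gating safety test.

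**What to change.** State in SAP 7.2.2 that imputation for both primary endpoints is done separately by randomised arm, or with arm as a predictor in every regression step, and adjust the worked example to show it. Site is in both ANCOVAs and is likewise absent from the imputation text. The same sentence can say whether it enters; the effect of omitting site was not evaluated here.

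The cost is one sentence and no new data. With arm as a predictor, the mean interval width rises from 1.86 to 1.88 g/L, or from 2.25 to 2.27. At a true difference of zero with spread dropout, simulated power falls from 98.0% to 96.3% (constant correlation 0.65) or from 88.6% to 86.0% (decaying 0.85), still above the planned 80%. Imputation separately by arm was not simulated.
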